#### 4.2.1 Primary

##### Safety

- The frequency, intensity, and duration of solicited local AEs on each vaccination day and the following 7 days.
- The frequency, intensity, duration, and relationship to trial vaccination of solicited systemic AEs on each vaccination day and the following 7 days.
- The occurrence, intensity and relationship to trial vaccination of unsolicited AEs on each vaccination day and the following 28 days.
- The occurrence and relationship to trial vaccination of SAEs and AESIs throughout the trial.

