### 10.3.5 Primary Analysis

#### 10.3.5.1 Primary Safety Analysis

The safety measurements will include:

2. AEs (type, intensity, frequency and relationship to trial vaccination), i.e., incidence and severity of AEs for both solicited local (injection site pain, redness, swelling, and itching) and solicited systemic events (fever, headache, fatigue, chills, myalgia, arthralgia, nausea/vomiting, and diarrhea) occurring on the day of vaccination and the following 7 days, and unsolicited events (occurring on the day of vaccination and the following 28 days).
3. SAEs and AESIs throughout the trial.

**Solicited AEs:** For reactogenicity assessment, the number and percentage of subjects with at least 1 solicited AE of any kind, by severity grade, for local, systemic, and overall, will be summarized after the first vaccination and after the second vaccination. For subjects with more than 1 episode of the same event, the maximum severity will be used for tabulations. In addition, the frequencies and severity of each solicited AE will be summarized for each vaccination day and the following 7 days. Similar tabulations will be

performed for solicited systemic AEs considered as related to the trial vaccine. The duration and severity of solicited AEs will be analyzed at subject level.

In addition, other indicators of safety (e.g., body temperature) will be collected and summarized. The number and percentage of subjects with Grade 3 adverse reaction(s) or SAEs considered as related to the trial vaccine according to the Investigator with the 95% CI based on the Beta (0.5, 0.5) prior distribution will be calculated and summarized.

**Unsolicited AEs:** Unsolicited AEs, SAEs and AESIs will be coded using the Medical Dictionary for Regulatory Activities (MedDRA) by System Organ Class (SOC) and Preferred Term (PT). The frequency and percentage of subjects reporting these events will be tabulated at the SOC and PT levels. Additional similar tabulations will be performed to evaluate severity and relationship to the trial vaccine. AEs that are reported as related to the trial vaccine will be considered trial vaccine-related; missing classifications concerning trial vaccine relationship will also be considered trial vaccine-related.

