7.1 Primary Objectives

- To evaluate the safety and reactogenicity profile after 1 and 2 dose administrations of CVnCoV.
- To evaluate the humoral immune responses 14 days after 2 dose administrations of CVnCoV.

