9.4 Estimands

Based on the Protocol Amendment #1, a subset of endpoints will be presented. See Section 6.1, 6.2, 6.3 and 6.4 and Appendix 4 List of Abbreviated Scope Based on SAP Version 2.0 for additional details.

ENDPOINTS (subject level)	ESTIMANDS (population level)
Primary Safety	

The frequency, intensity, and duration of solicited local AEs on each vaccination day and the following 7 days.
 
The frequency, intensity, duration, and relationship to trial vaccination of solicited systemic AEs on each vaccination day and the following 7 days.
 
The occurrence, intensity and relationship to trial vaccination of unsolicited AEs on each vaccination day and the following 28 days.
 
The occurrence and relationship to trial vaccination of SAEs and AESIs throughout the trial.
	
In subjects who received at least one dose of CVnCoV vaccine and a post baseline vaccine safety assessment is available. Subjects receiving an authorized/licensed COVID-19 vaccine during the course of the trial will be censored at the day after intake. The primary safety will be analyzed with the safety analysis set.
 
The number and percentage of subjects overall and by co-morbidity:
 
Each solicited local AE within 7 days (after each trial vaccination by intensity and overall).
 
Each solicited systemic AE within 7 days after each trial vaccination by intensity, by relationship to trial vaccine and overall.
 
The mean duration in days by group with standard deviation of solicited AEs (within the solicited period, total duration).
 
At least 1 unsolicited AEs, at least 1 grade unsolicited AEs and each unsolicited AEs by SOC/PT occurring within 28 days after each trial vaccination and overall by causal relationship to trial vaccine and overall.
 
At least 1 SAE, or at least 1 AESI to vaccine overall by causal relationship to trial vaccine and overall.

ENDPOINTS (subject level)	ESTIMANDS (population level)
Primary Immunogenicity	

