10.7.2.1.1 Duration of Solicited Adverse Events

Duration of solicited local and systemic adverse events are defined as the sum consecutive days with local/systemic adverse events (days 1 to 8) for the same grade. For example, Fatigue with grade 1 occurring on day 2 and 3 and day 7 will be counted as two separate events with the duration 2 days and 1 day. For the duration of solicited local and systemic AEs ongoing beyond Day 8 the following definition is used:

If the AE is present on day 8 in the diary and the same AE is present on day 9 on the eCRF, the sum of days between the date of day 9 and end date for the AE on the eCRF is added to the consecutive days as collected on the diary. If the duration of any AE continues after the next dose and the subject experience an AE of the same type in the second dose, these two events will be presented separately.

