12.7.1.2 Analysis of Solicited AEs

The following summaries of solicited AEs within 7 days after each trial vaccination and within 7 days after any trial vaccination will be provided. If not stated otherwise the maximum grade will be presented (grade 0 to grade 3).

- Summary of solicited AEs, local AEs and systemic AEs, overall and by maximum grade
- Summary of local AEs, overall and by maximum grade
- Summary of systemic AEs, overall and by maximum grade (occurrence of systemic AEs will also be presented from day -7 until day -1)*
- Summary of related systemic AEs, overall and by maximum grade*
- Duration (days) of solicited AEs, overall and for Grade 3 events
- Duration (days) of local AEs, overall and for Grade 3 events*
- Duration (days) of systemic AEs, overall and for Grade 3 events*
- Duration (days) of related systemic AEs, overall and for Grade 3 events*
- Daily summary of local AEs (only for each dose)*
- Daily summary of systemic AEs (only for each dose)*
- Daily summary of related systemic AEs (only for each dose)*
- Summary of time of onset (Day) for grade 3 solicited AEs, any solicited AEs, local, systemic AEs, and related systemic AEs*
- Time of onset (Day) of local AEs*
- Time of onset (Day) of systemic AEs*
- Time of onset (Day) of related systemic AEs*
- Individual grade 3 solicited local and systemic adverse events will be presented in a figure.*

In addition, number and percentage of subjects with solicited Grade 3 adverse reaction(s) or SAEs considered as related to the trial vaccine according to the Investigator with the 95% credibility interval based on the Beta (0.5, 1.5) prior distribution will be calculated and summarized. This analysis is not part of the abbreviated scope.

Solicited AEs occurring on the day of vaccination and the following 7 days will be listed separately as well.

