14.3.2 Adverse Events Data Tables
Table 14.3.2.1.1 Overall Summary of Adverse Events (Safety Analysis Set)
Table 14.3.2.2.1 Summary of Solicited Adverse Events and Maximum Grade Occurring on the Day of Vaccination and the following 7 Days after any Dose (Safety Analysis Set)
Table 14.3.2.3.1 Local Solicited Adverse Events and Maximum Grade Occurring on the Day of Vaccination and the following 7 Days after any Dose (Safety Analysis Set)
Table 14.3.2.4.1 Systemic Solicited Adverse Events and Maximum Grade Occurring on the Day of Vaccination and the following 7 Days after any Dose (Safety Analysis Set)
Table 14.3.2.6.1 Duration of Solicited Adverse Events Occurring on the Day of Vaccination and the following 7 Days after any Dose (Safety Analysis Set)

Table 14.3.2.16.1 Unsolicited Adverse Events by System Organ Class and Preferred Term Occurring on the Day of Vaccination and the following 28 Days after any Dose (Safety Analysis Set)
Table 14.3.2.16.2 Unsolicited Adverse Events by System Organ Class and Preferred Term Occurring on the Day of Vaccination and the following 28 Days after Dose 1 (Safety Analysis Set)
Table 14.3.2.16.3 Unsolicited Adverse Events by System Organ Class and Preferred Term Occurring on the Day of Vaccination and the following 28 Days after Dose 2 (Safety Analysis Set)
Table 14.3.2.17.1 Unsolicited Adverse Events for Duration of Trial by System Organ Class and Preferred Term (Safety Analysis Set)
Table 14.3.2.17.2 Related Unsolicited Adverse Events for Duration of Trial by System Organ Class and Preferred Term (Safety Analysis Set)
Table 14.3.2.20.1 Unsolicited Adverse Events by System Organ Class, Preferred Term, and Maximum Severity Occurring on the Day of Vaccination and the following 28 Days after any Dose (Safety Analysis Set)
Table 14.3.2.20.2 Unsolicited Adverse Events by System Organ Class, Preferred Term, and Maximum Severity Occurring on the Day of Vaccination and the following 28 Days after Dose 1 (Safety Analysis Set)
Table 14.3.2.20.3 Unsolicited Adverse Events by System Organ Class, Preferred Term, and Maximum Severity Occurring on the Day of Vaccination and the following 28 Days after Dose 2 (Safety Analysis Set)
Table 14.3.2.26.1 Adverse Events of Special Interest for Duration of Trial by System Organ Class and Preferred Term (Safety Analysis Set)
Table 14.3.2.29.1 Adverse Events Leading to Study Withdrawal by System Organ Class and Preferred Term (Safety Analysis Set)

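### SAP Appendix 4 lists the solicited-AE tables only for any dose, although the protocol and SAP plan solicited-AE occurrence after each vaccination, and SAP 6.4 neither states nor justifies the change

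*SAP*

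**What the plan says.** The primary objective, kept in SAP 7.1, is "To evaluate the safety and reactogenicity profile after 1 and 2 dose administrations of CVnCoV". The first primary safety endpoint in protocol 4.2.1 is "The frequency, intensity, and duration of solicited local AEs on each vaccination day and the following 7 days"; the systemic endpoint has the same window.

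The planned analyses follow from this:

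- Protocol 10.3.5.1: numbers and percentages of subjects with solicited AEs by grade, "for local, systemic, and overall, will be summarized after the first vaccination and after the second vaccination".
- SAP 9.4: the local and systemic estimands are set after each vaccination. The systemic one reads "Each solicited systemic AE within 7 days after each trial vaccination by intensity, by relationship to trial vaccine and overall".
- SAP 12.7.1: unless stated otherwise, AE occurrence in a defined period after a dose is shown for any dose, dose 1 and dose 2.
- SAP 12.7.1.2: "The following summaries of solicited AEs within 7 days after each trial vaccination and within 7 days after any trial vaccination will be provided". The list under this sentence includes overall, local and systemic summaries and duration.

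Appendix 4, which holds the outputs of the abbreviated scope, is narrower. Its solicited-AE tables are 14.3.2.2.1 (all), 14.3.2.3.1 (local), 14.3.2.4.1 (systemic) and 14.3.2.6.1 (duration), and every title is for any dose; the first reads "Table 14.3.2.2.1 Summary of Solicited Adverse Events and Maximum Grade Occurring on the Day of Vaccination and the following 7 Days after any Dose". In the same section the unsolicited families 14.3.2.16 and 14.3.2.20 each have three versions; one title is "Unsolicited Adverse Events by System Organ Class and Preferred Term Occurring on the Day of Vaccination and the following 28 Days after Dose 2".

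**The concern.** If the tables are programmed as titled, the abbreviated report has no summary of solicited reactions after the first dose or after the second. That split is part of the primary safety endpoint; it is not an optional subgroup.

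An any-dose table counts each subject once, at the highest grade over whichever doses were given. It cannot show whether reactions were more frequent or more severe after one dose than after the other. It can also mix subjects who had one dose with subjects who had two: note b to SAP Table 2 foresees subjects without a second injection, and the individual stopping rules in SAP 8.2.1 withhold the second dose after certain related reactions. Second-dose recipients may therefore be a selected group, which a pooled table hides.

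A reader who compares the report with protocol 10.3.5.1 would find a planned primary summary absent, with no reason given.

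**Working it through.** The documents give no event counts, so the check is a count of the listed tables, a comparison of sources, and a short argument on what an any-dose table can show.

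**Step 1. Count the tables in Appendix 4, section 14.3.2.**

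- Solicited: 4 = 4 any dose + 0 Dose 1 + 0 Dose 2.
- Unsolicited, 28-day window (14.3.2.16.1 to .3 and 14.3.2.20.1 to .3): 6 = 2 any dose + 2 Dose 1 + 2 Dose 2.

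**Step 2. Find which source calls for a split by dose, table by table.**

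| Appendix 4 table | Protocol 10.3.5.1 | SAP 9.4 estimand | SAP 12.7.1 default | SAP 12.7.1.2 |
|---|---|---|---|---|
| 14.3.2.2.1 all | yes | no estimand for any solicited AE taken together | yes | yes |
| 14.3.2.3.1 local | yes | yes | yes | yes |
| 14.3.2.4.1 systemic | yes | yes | yes | unclear |
| 14.3.2.6.1 duration | no: subject level only | no dose split | yes, though worded for occurrence outputs | yes |

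The systemic entry is unclear because that bullet ends with the asterisk for analyses outside the abbreviated scope. The asterisk follows a parenthesis on the week before vaccination, so it may cover only that part. Table 14.3.2.4.1 is in Appendix 4 all the same.

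**Step 3. Look for a statement that the split is dropped.** Besides its general scope item, SAP 6.4 names five changes: the credibility interval for Grade 3 reactions or related SAEs, the analysis set for secondary immunogenicity, cell-mediated immunity, confirmed COVID-19 cases, and time points up to Day 120. None concerns solicited AEs by dose. The scope item keeps the occurrence and duration of solicited AEs among the key analyses. SAP 6.3, 9.4 and 12.7 refer to Appendix 4 in general terms.

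**Step 4. Ask whether rates by dose can be recovered.** Let p1 and p2 be the proportions reacting after dose 1 and dose 2, and p the proportion reacting after any dose, with a common denominator. Then

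max(p1, p2) ≤ p ≤ p1 + p2.

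Given p alone, each of p1 and p2 can lie anywhere from 0 to p, provided that they sum to at least p. The same holds at any grade threshold, because the table uses the maximum grade. If fewer subjects receive dose 2, the exposure table (14.3.1.1) can supply that denominator, but the number who reacted after dose 2 remains unknown.

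**Step 5. Look for another listed summary.** The daily solicited summaries that SAP 12.7.1.2 plans for each dose are asterisked, and no table in Appendix 4 has such a title. Listings 16.2.7.2 and 16.2.7.3 keep the subject-level local and systemic data.

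**The case against.** The strongest reply is that Appendix 4 is itself the declaration. SAP 6.3 says that the changes are described there, SAP 9.4 announces a subset of endpoints, and SAP 12.7 presents the text below it as the version 1.0 plan. SAP 6.4 gives the reduced sample size as the reason for an abbreviated report; 129 of 1,200 planned subjects were enrolled, and the analysis is descriptive only. This stands in part: the change can be inferred from the titles. But no sentence states it, and the sample-size reason is not tied to it. The unsolicited tables by system organ class and preferred term divide the same subjects more finely, yet keep the split. The after-each-vaccination estimands remain in SAP 9.4, and the amendment text does not alter protocol 10.3.5.1.

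Second, the table shells are a separate document (SAP 10.0), so dose columns may exist under an any-dose title. Table 14.3.2.1.1 has no dose wording, although SAP 12.7.1.1 plans that summary by dose. This cannot be excluded. The .1, .2, .3 numbering of the unsolicited families argues against it.

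Third, SAP 12.7 says that analyses not performed will be described. This could mean only that they stay in the text, so it is not relied on as a promise to itemise each one.

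**Conclusion.** The point holds. As titled, 4 of 4 solicited-AE tables lack a version by dose, against protocol 10.3.5.1 for the three occurrence tables, and SAP 6.4 neither states nor justifies this. It should be corrected before the tables are produced. It is a gap in the listed summaries, not in the data.

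The documents do not support four stronger readings:

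- A reader might infer that protocol 10.3.5.1, SAP 9.4 and SAP 12.7.1.2 all require the split for all four tables. Only the local table has clear support from all three, and duration rests on SAP 12.7.1.2 and the 12.7.1 default.
- A reader might count eight missing tables (4 × 2). That number assumes that the unseen shells contain no dose columns.
- A reader might take SAP 10.7.2.1.1, under which, if "the subject experience an AE of the same type in the second dose, these two events will be presented separately", as a plan for tables by dose. It is a rule for counting episodes.
- A reader might expect a bias of known size. The documents give no event counts and no number of one-dose subjects, so the difference between the doses cannot be computed.

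**What to change.** In SAP Appendix 4, add Dose 1 and Dose 2 versions of the three occurrence tables (14.3.2.2, 14.3.2.3 and 14.3.2.4), numbered .2 and .3 as for 14.3.2.16, with recipients of that dose as denominator. Add the same two versions of the duration table (14.3.2.6), for consistency with SAP 12.7.1.2. This makes up to 3 × 2 + 1 × 2 = 8 further outputs. If the shells already have dose columns, correct the four titles instead.

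If the sponsor means to leave the split out, SAP 6.4 should say so with the reason, and SAP 9.4 and 12.7.1.2 should be aligned. That would end the silence, but the primary objective would still have no summary by dose.

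The cost is small: repeat runs of four tables that are produced anyway, from data already collected. The downside is a slightly longer abbreviated report with sparse co-morbidity strata.

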12.7 Analyses

The primary, secondary and exploratory endpoints will be analyzed overall, as well as per underlying comorbidity.

Based on the Protocol Amendment #1, a subset of analyses will be presented. See Section 6.1, 6.2, 6.3, 6.4 and Appendix 4 List of Abbreviated Scope Based on SAP Version 2.0 for additional details. Below all planned analyses according to SAP version 1.0 will be described. Any analysis not performed according to the abbreviated scope will be described.

Any analysis marked with an asterisk * will not be part of the abbreviated scope described in detail in Appendix 4.

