12.7.1.1 Analysis of Unsolicited AEs and Solicited AEs

An overall summary of unsolicited AEs will be prepared for AEs occurring within 28 days after each dose, within 28 days after any dose, and all reported AEs (including those reported at more than 28 days after any dose).

- Unsolicited AEs
- Related unsolicited AEs
- SAEs (includes solicited AEs)
- Related SAEs (includes solicited AEs)
- Grade 3 (severe) unsolicited AEs
- Grade 3 (severe) related unsolicited AEs
- Intercurrent medical conditions affecting immune response (includes solicited AEs)
- Medically attended AEs (includes solicited AEs)
- Related medically attended AEs (includes solicited AEs)
- AESIs (includes solicited AEs)
- Related AESIs (includes solicited AEs)
- Medically attended AEs (includes solicited AEs)
- Related medically attended AEs (includes solicited AEs)
- AESIs (includes solicited AEs)
- Related AESIs (includes solicited AEs)
- AEs leading to vaccine withdrawal
- AEs leading to withdrawal from trial

The overall summary will also be presented for overall and by sex (female/male)* and for any dose (dose 1 and dose 2) and include AEs for the duration of the trial.

The following summaries of unsolicited AEs by SOC and PT will further be provided, separately for AEs occurring within the first 28 days after each vaccination, within the 28 days after any vaccination, and all reported AEs (including those reported at more than 28 days after any dose) if not otherwise stated:

- Occurrence of unsolicited AEs
- Occurrence of related unsolicited AEs*
- Occurrence of SAEs (includes solicited AEs)*
- Occurrence of related SAEs (includes solicited AEs) *
- Occurrence of unsolicited AEs by maximum severity (mild / moderate / severe)*
- Occurrence of related unsolicited AEs by maximum severity (mild / moderate / severe) *
- Occurrence of SAEs by maximum severity (mild / moderate / severe) (includes solicited AEs)*

- Occurrence of related SAEs by maximum severity (mild / moderate / severe) (includes solicited AEs)*
- Occurrence of AESIs (includes solicited AEs)
- Occurrence of related AESIs (includes solicited AEs)*
- Occurrence of intercurrent medical conditions affecting immune response (includes solicited AEs)*
- Occurrence of medically attended AEs (includes solicited AEs)*
- Occurrence of related medically attended AEs (includes solicited AEs)*
- Occurrence of AEs leading to withdrawal from trial (includes solicited AEs)

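### SAP Appendix 4 tabulates related unsolicited AEs by SOC/PT only for the whole trial, although the primary estimand also asks for them within 28 days after each dose

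*SAP*

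**What the plan says.** Protocol 4.2.1 defines the primary safety endpoint for unsolicited AEs as "The occurrence, intensity and relationship to trial vaccination of unsolicited AEs on each vaccination day and the following 28 days". Protocol 10.3.5.1, after promising SOC and PT tabulations, adds: "Additional similar tabulations will be performed to evaluate severity and relationship to the trial vaccine".

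The estimand in SAP 9.4 asks for the number and percentage of subjects with "each unsolicited AEs by SOC/PT occurring within 28 days after each trial vaccination and overall by causal relationship to trial vaccine and overall".

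SAP 12.7.1.1 plans the SOC/PT summaries of unsolicited AEs "separately for AEs occurring within the first 28 days after each vaccination, within the 28 days after any vaccination, and all reported AEs". One of the items is "Occurrence of related unsolicited AEs", and it carries an asterisk. SAP 12.7 explains the mark: "Any analysis marked with an asterisk * will not be part of the abbreviated scope described in detail in Appendix 4".

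Appendix 4, the list of outputs for the abbreviated report on 129 enrolled subjects, contains one related-only SOC/PT table for unsolicited AEs: "Table 14.3.2.17.2 Related Unsolicited Adverse Events for Duration of Trial by System Organ Class and Preferred Term (Safety Analysis Set". It also keeps the overall summary (Table 14.3.2.1.1) and the AE listing (Listing 16.2.7.1).

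**The concern.** The endpoint has three components that share one window. Two of them keep their 28-day, per-dose SOC/PT tables in the abbreviated scope. The third, relationship, keeps only a trial-long table.

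This matters because the trial is single-arm and enrols adults with chronic disease. All-cause tables after Dose 1 and Dose 2 will contain background illness as well as reactions. The investigator's causality assessment is the main device in the plan for separating the two. The primary objective is the safety profile after one and after two doses (Protocol 4.1.1, SAP 7.1). A reader of the listed tables could see how many subjects had a related unsolicited AE after each dose, but not what those events were.

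The related table also covers a different period from the occurrence and severity tables, so the three cannot be read line by line against each other.

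**Working it through.** The plan gives no figure to reproduce. The check is a comparison of the listed outputs with the endpoint, followed by a count of days.

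**Step 1. SOC/PT tables for unsolicited AEs in Appendix 4, by component and window**

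| Component | 28 days, any dose | 28 days, Dose 1 | 28 days, Dose 2 | Duration of trial |
|---|---|---|---|---|
| Occurrence | 14.3.2.16.1 | 14.3.2.16.2 | 14.3.2.16.3 | 14.3.2.17.1 |
| Maximum severity | 14.3.2.20.1 | 14.3.2.20.2 | 14.3.2.20.3 | none |
| Relationship | none | none | none | 14.3.2.17.2 |

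SAP 12.7.1.1 plans four windows for related events by SOC/PT: Dose 1, Dose 2, any dose, and all reported. Appendix 4 keeps 1 of 4, the last.

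**Step 2. What the overall summary still gives.** Under SAP 12.7.1.1 it is prepared for AEs within 28 days after each dose, within 28 days after any dose, and for all reported AEs. Its rows without an asterisk include related unsolicited AEs and Grade 3 related unsolicited AEs. Only the presentation by sex is asterisked. So relationship is counted per dose in the right window, but without SOC or PT.

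**Step 3. Is the cut declared?** SAP 6.4 itemises the reductions, such as the Grade 3 credibility interval and CMI. It names unsolicited AEs among the key analyses retained and does not mention this omission. SAP 9.4 notes other dropped items beside their estimands (Day 211 and Day 393, CMI), but puts no note on the unsolicited-AE estimand. The asterisk in 12.7.1.1 does point to a cut. It is not a dependable signal, because two asterisked items reappear in Appendix 4: related unsolicited AEs (14.3.2.17.2) and unsolicited AEs by maximum severity (14.3.2.20.1 to 14.3.2.20.3).

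**Step 4. How far the trial-long window differs from the endpoint window.** The inputs are the vaccination day plus 28 days (Protocol 4.2.1), a dose 2 visit window of -3/+14 days, and an end of trial at dose 2 + 91 days, or at Day 91 after one dose only (amended schedule, Tables 1 and 2). I assume the last visit falls exactly on its nominal day. Days outside = follow-up days minus days covered by the 28-day windows.

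| Case | Days covered | Follow-up | Outside |
|---|---|---|---|
| Dose 2 on Day 29 | Days 1–57: 57 | 120 | 120 − 57 = 63 (52.5%) |
| Dose 2 on Day 26 | Days 1–54: 54 | 26 + 91 = 117 | 117 − 54 = 63 (53.8%) |
| Dose 2 on Day 43 | 29 + 29 = 58 | 43 + 91 = 134 | 134 − 58 = 76 (56.7%) |
| One dose only | Days 1–29: 29 | 91 | 91 − 29 = 62 (68.1%) |

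These are shares of calendar days, not of events. Diary collection of unsolicited AEs stops 28 days after each dose (SAP 10.7.3), so the share of related events outside the window is probably smaller.

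**The case against.** The strongest case on the other side has five parts.

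- **Relationship is already reported by dose in the window.** The overall summary does this, and the protocol endpoint itself does not mention SOC/PT. This stands. A reader who looks only at the SOC/PT tables might infer that the plan has no per-dose relationship result, or only one trial-wide count. SAP 12.7.1.1 contradicts that inference. The gap is at SOC/PT level, and the requirement for that level comes from SAP 9.4.
- **The estimand also says overall.** Its wording is awkward, and Table 14.3.2.17.2 answers the overall part. This stands, but the same sentence names the 28 days after each vaccination, and that part has no related SOC/PT table.
- **The cut is disclosed.** The asterisk, the statement in 9.4 that only a subset of endpoints is presented, and the drop from 1,200 to 129 subjects all point to a deliberate reduction in a descriptive trial. This stands in part. A reduced scope is legitimate, but it does not explain keeping per-dose tables for two components and not the third, and Appendix 4 does not follow the asterisks.
- **The window difference is small in practice.** Events collected through the whole trial are mainly SAEs, AESIs, intercurrent conditions, medically attended AEs and AEs leading to withdrawal. This is plausible. It does not supply the split by dose.
- **The detail can be recovered.** The AE listing and the dosing listing (16.2.5.1) are kept, and 129 subjects can be traced by hand. This is true, but a listing is not the number and percentage that the estimand specifies.

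One limit applies to the criticism as well. That Table 14.3.2.17.2 has no dose split is read from its title; the table shells are a separate document. The neighbouring 28-day tables do state their dose in the title.

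**Conclusion.** The point holds at SOC/PT level. Appendix 4 does not deliver the per-dose, 28-day relationship part of the unsolicited-AE estimand in SAP 9.4. Three of the four windows planned for related events by SOC/PT are absent, and SAP 6.4 does not say so. What is lost is the identity of the related event terms after each dose, as number and percentage. The per-dose count of subjects with any related unsolicited AE is not lost.

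Separately, SAP 12.7.1.1 and Appendix 4 contradict each other on whether related and maximum-severity summaries are in scope, and this needs correcting in any case.

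No test, interval or sample size is affected. The conclusion rests on reading table titles as complete descriptions of their content, and on Table 14.3.2.1.1 being produced with the windows and rows that 12.7.1.1 describes. It is a modest reporting gap in a primary safety endpoint, worth closing because closing it is nearly free.

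**What to change.** 1. Add to Appendix 4 related-only versions of Tables 14.3.2.16.2 (Dose 1) and 14.3.2.16.3 (Dose 2), and of 14.3.2.16.1 (any dose) for completeness, with the same window, layout and denominators as the parent tables.
2. Keep Table 14.3.2.17.2 as the trial-long supplement.
3. Align the asterisks in SAP 12.7.1.1 with Appendix 4, for both related unsolicited AEs and unsolicited AEs by maximum severity.
4. If the per-dose related tables are left out on purpose, say so in SAP 6.4 and beside the estimand in SAP 9.4, and refer the reader to the overall summary and the AE listing.

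The cost is up to three tables from an existing program with a relationship filter, plus a short text edit. No new data are needed.
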